10.1.8. Inspections

The investigator should understand that source documents for this trial should be made available to appropriately qualified personnel from Gilead Sciences or its representatives, to IRB/IECs, and to regulatory authority or health authority inspectors. It is important that the investigator and relevant institutional personnel are available during monitoring visits and possible audits or inspections and that sufficient time is devoted to the process.

10.1.9. Protocol Compliance

The investigator is responsible for ensuring the study is conducted in accordance with the procedures and evaluations described in this protocol.

10.2. Sponsor Responsibilities

10.2.1. Protocol Modifications

Protocol modifications, except those intended to reduce immediate risk to study subjects, will be made only by Gilead Sciences. All protocol modifications must be submitted to the IRB/IEC in accordance with local requirements. Except as noted in Section 10.1.2, IRB/IEC approval must be obtained before changes can be implemented.

10.2.2. Communications with Regulatory Authorities

Gilead Sciences, working either directly or through designees, will assume responsibility for regulatory interactions with relevant regulatory authorities. Gilead Sciences will maintain an IND for idelalisib in support of the study in the United States and will maintain similar regulatory applications with other regulatory authorities, as required for conduct of the study. In fulfilling this responsibility, Gilead Sciences (or a designee) will collect, assemble, and communicate all required regulatory documents (eg, Form FDA 1572, investigator financial disclosure forms, protocol and protocol amendments, investigator brochures, informed consent documents, annual reports) as required by regulation. Gilead Sciences (or a designee) will also assume responsibility for adverse event reporting to regulatory authorities as described in Section 8.7.2.

10.2.3. Data Management

Electronic data capture will be used to enter study data eCRFs and to transfer the data into a study-specific electronic database. During the data collection process, automated quality assurance programs will be used to identify missing data, selected protocol violations, out-of-range data, and other data inconsistencies. Requests for data clarification or correction will be forwarded to the investigative site for resolution. As appropriate, eCRFs, listings, tables, and SAS datasets will be provided to the investigational sites for review.

Quality assurance and quality control systems will be implemented and maintained according to written standard operating procedures to ensure that the data are generated, recorded, and reported in compliance with the protocol, GCP, and applicable regulatory requirements. Data collection and storage systems will provide audit trail, security mechanisms, and electronic signature capabilities that meet the requirements of FDA Title 21 of CFR Part 11 regarding electronic records and electronic signatures.

Data security will be controlled through appropriate and specific restriction of access only to data and systems required by individual users to accomplish their roles in the data management process. Individual login and password protections will be employed at study sites and at Gilead Sciences or its designee. The database will exist on physically secured servers. Data backups will be done regularly and will be stored in separate facilities. Printed documents relating to the study will be secured when not under review.

10.2.4. Study Reporting and Publication

Gilead Sciences may make information obtained during this study available in order to further the scientific or business needs of the company or as required by law or regulation. In this regard, Gilead Sciences may provide study information to private or public organizations (eg, business partners, collaborators, consultants, CROs, investors, other physicians who are conducting similar studies, funding organizations, regulatory authorities, or other government authorities).

Gilead Sciences will prepare a clinical study report for submission to relevant regulatory agencies. Gilead Sciences will ensure that the report meets the standards set out in the ICH Guideline for Structure and Content of Clinical Study Reports (ICH E3). An abbreviated report may be prepared in certain cases, as appropriate.

Gilead Sciences intends that the data from this study will be presented and published. Gilead Sciences will work in collaboration with the principal investigators in preparing presentations and writing manuscripts for publication.

• Investigators may publish or present the results of the study generated by their individual site either with the advanced written consent of Gilead or > 2 years after the completion of this extension study (GS-US-312-0117) at all participating institutions.

No such communication, presentation, or publication will include Gilead Sciences' confidential information (see Section 10.1.4).

The investigator will submit to Gilead Sciences any proposed publication or presentation along with the respective scientific journal or presentation forum prior to submission of the publication (at least 30 days prior to manuscripts and 15 days prior for abstracts and oral presentations). The investigator will comply with Gilead Sciences' request to delete references to its confidential information (other than the study results) in any paper or presentation. If deemed necessary by Gilead Sciences, the investigator also agrees to withhold publication or presentation for an additional 60 days in order to obtain patent protection.

10.3. Joint Investigator/Sponsor Responsibilities

10.3.1. Access to Information for Monitoring

In accordance with ICH Good Clinical Practice (ICH GCP) guidelines, the study monitor must have direct access to the investigator's source documentation in order to verify the data recorded in the eCRFs for consistency.

The monitor is responsible for routine review of the eCRFs at regular intervals throughout the study to verify adherence to the protocol and the completeness, consistency, and accuracy of the data being entered on them. The monitor should have access to any subject records needed to verify the entries on the eCRFs. The investigator agrees to cooperate with the monitor to ensure that any problems detected in the course of these monitoring visits are resolved.

10.3.2. Access to Information for Auditing or Inspections

Representatives of regulatory authorities or of Gilead Sciences may conduct inspections or audits of the clinical study. If the investigator is notified of an inspection by a regulatory authority the investigator agrees to notify the Gilead Sciences medical monitor immediately. The investigator agrees to provide to representatives of a regulatory agency or Gilead Sciences access to records, facilities, and personnel for the effective conduct of any inspection or audit.

10.3.3. Public Notification of Study Conduct

Consistent with Section 113 of the Food and Drug Modernization Act of 1997 (FDAMA) and with requirements of the International Committee of Medical Journal Editors (ICMJE) as a condition of consideration for publication of study results, Gilead Sciences will be responsible for ensuring that this protocol is listed at the ClinicalTrials.gov website (or equivalent) and that information at the website relating to study design and conduct is appropriately updated during the course of the study. In order to facilitate this process, investigators will need to supply Gilead Sciences with appropriate contact information for study site personnel.

10.3.4. Study Discontinuation

Both the sponsor and the investigator reserve the right to terminate the study at any time. Should this be necessary, both parties will arrange discontinuation procedures and notify the appropriate regulatory authorities and IRB/IECs. In terminating the study, Gilead Sciences and the investigator will assure that adequate consideration is given to the protection of the subjects' interests.

10.4. Study Committees

10.4.1. Data Monitoring Committee

A DMC, operating autonomously from Gilead Sciences, the clinical investigators, and the SSC, will be responsible for providing independent recommendations to Gilead Sciences about evolving risk-benefit observed in the course of the study and any modifications required during the course of the study. The DMC will consist of a biostatistician and ≥2 physicians experienced in treating patients with lymphoid malignancies. The DMC will be chaired by one of these individuals. DMC members must not be actively involved in study design, conduct, or subject accrual and must not have financial, proprietary, professional, or other interests that may affect impartial, independent decision-making. Specialists may be invited to participate as non-voting members at any time if additional expertise is desired. The DMC will formally interact with the external SSC members through the sharing of meeting minutes. Informal interactions between the DMC and external SSC members will be limited. The DMC will operate under a charter developed as a collaborative document between Gilead Sciences and the DMC. It is expected that the members of the DMC will be the same as those for the primary study (Study GS-US-312-0116).

The primary responsibility of the DMC is to protect the safety and welfare of subjects participating in this clinical trial and to ensure the integrity of the clinical trial. In general, the DMC will be responsible for:

- Reviewing the general progress of the study as regards subject accrual, study conduct, and protocol violations
- Examining accumulated safety, efficacy, and other relevant data at prespecified points during the course of the study
- Reviewing major study design modifications prior to implementation of those modifications
- Making recommendations concerning continuation, modification, interruption, or termination of each study
- Advising the company on changes to informed consent documents
- Proposing updates to the DMC monitoring plan, changes in the DMC membership, actions to be taken relating to conflict of interest or confidentiality breaches, the need for additional expertise during DMC deliberations, revisions to the DMC charter, or alterations in the support provided to the DMC
- Providing expert advice to the Gilead Science medical monitor on an ad hoc basis regarding matters such as safety concerns or diagnostic evaluations in individual subjects

Based on the results of its deliberations during the course of the study, the DMC can recommend appropriate actions (eg, continuation of the study unchanged, continuation of the study with modifications in design or monitoring plan, interruption of study accrual, study termination).

10.4.2. Independent Review Committee

An IRC will be established to provide a blinded review of radiographic data and pertinent clinical data in order to provide expert interpretation of changes in tumor status. The IRC will include ≥1 independent board-certified radiologist and ≥1 independent board-certified hematologist or oncologist, and will be managed by a CRO selected by Gilead Sciences. The review of radiographic and clinical data by the IRC will be performed on an ongoing basis until the primary analysis. The specifics of the IRC's processes and reading methods will be described in an independent review charter developed by the contracted imaging facility in conjunction with Gilead Sciences. The same organization that is providing IRC services for Study GS-US-312-0116 will provide IRC services for this study.

Appendix 2. Functional Assessment of Cancer Therapy: Leukemia (FACT-Leu)

FACT-Leu (Version 4)

Below is a list of statements that other people with your illness have said are important. Please circle or mark one number per line to indicate your response as it applies to the past 7 days.

	PHYSICAL WELL-BEING	Not at all	A little bit	Some- what	Quite a bit	Very much
GP1	I have a lack of energy	0	1	2	3	4
GP2	I have nausea	0	1	2	3	4
GP3	Because of my physical condition, I have trouble meeting the needs of my family	0	1	2	3	4
GP4	I have pain	0	1	2	3	4
GP5	I am bothered by side effects of treatment	0	1	2	3	4
GP6	I feel ill	0	1	2	3	4
GP7	I am forced to spend time in bed	0	1	2	3	4
	SOCIAL/FAMILY WELL-BEING	Not at all	A little bit	Some- what	Quite a bit	Very much
GS1	I feel close to my friends	0	Ĭ	2	3	4
GS2	I get emotional support from my family	0	1	2	3	4
GS3	I get support from my friends	0	1	2	3	4
GS4	My family has accepted my illness	0	1	2	3	4
GS5	I am satisfied with family communication about my illness.	0	1	2	3	4
GS6	I feel close to my partner (or the person who is my main support)	0	1	2	3	4
QI	Regardless of your current level of sexual activity, please answer the following question. If you prefer not to answer it, please mark this box and go to the next section.					
GS7	I am satisfied with my sex life	0	1	2	3	4

English (Universal)

Controlled 1087 1007

FACT-Leu (Version 4)

Please circle or mark one number per line to indicate your response as it applies to the past 7 days.

	EMOTIONAL WELL-BEING	Not at all	A little bit	Some- what	Quite a bit	Very much
GE1	I feel sad	0	1	2	3	4
GE2	I am satisfied with how I am coping with my illness	0	1	2	3	4
GE3	I am losing hope in the fight against my illness	0	1	2	3	4
GE4	I feel nervous	0	1	2	3	4
GE5	I worry about dying	0	1	2	3	4
GE6	I worry that my condition will get worse	0	1	2	3	4
	FUNCTIONAL WELL-BEING	Not at all	A little bit	Some- what	Quite a bit	Very much
GF1	FUNCTIONAL WELL-BEING I am able to work (include work at home)	at all			1000	
GF1		at all	bit	what	a bit	much
7,553,50	I am able to work (include work at home)	0 0	bit	what	a bit	much
GF2	I am able to work (include work at home)	0 0 0	bit 1	what 2 2	a bit 3 3	4 4
GF2 GF3	I am able to work (include work at home)	0 0 0 0 0	1 1 1	2 2 2	3 3 3	4 4 4
GF2 GF3 GF4	I am able to work (include work at home)	0 0 0 0	bit 1 1 1 1	what 2 2 2 2 2	3 3 3 3 3	4 4 4 4

 English (Universal)
 19 November 200

 Copyright 1987, 1997
 Page 2 of

FACT-Leu (Version 4)

Please circle or mark one number per line to indicate your response as it applies to the past 7 days.

	ADDITIONAL CONCERNS	Not at all	A little bit	Some- what	Quite a bit	Very much
BRM3	I am bothered by fevers (episodes of high body temperature)	0	1	2	3	4
P2	I have certain parts of my body where I experience pain	0	1	2	3	4
BRM2	I am bothered by the chills	0	1	2	3	4
ES3	I have night sweats	0	1	2	3	4
LEUI	I am bothered by lumps or swelling in certain parts of my body (e.g., neck, armpits, or groin)	0	1	2	3	4
THI	I bleed easily	0	1	2	3	4
TH2	I bruise easily	0	1	2	3	4
HII12	I feel weak all over	0	1	2	3	4
BMT6	I get tired easily	0	1	2	3	4
C2	I am losing weight	0	1	2	3	4
C6	I have a good appetite	0	1	2	3	4
An7	I am able to do my usual activities	0	1	2	3	4
N3	I worry about getting infections	0	1	2	3	4
LEU5	I feel uncertain about my future health	0	1	2	3	4
LEU6	I worry that I might get new symptoms of my illness	0	1	2	3	4
BRM9	I have emotional ups and downs	0	1	2	3	4
LEU7	I feel isolated from others because of my illness or treatment	0	1	2	3	4

 English (Universal)
 19 November 200

 Copyright 1987, 1997
 Page 3 of

Appendix 3. Performance Status Scoring System

	Karno	ofsky Performance Status				
General Description	Score	Specific Description				
	100	Normal; no complaints; no evidence of disease.				
Able to carry on normal activity and to work; no special care needed.	90	Able to carry on normal activity; minor signs or symptoms of disease.				
	80	Normal activity with effort; some signs or symptoms of disease.				
Unable to work; able to live at home	70	Cares for self; unable to carry on normal activity or to do active work.				
and care for most personal needs; varying amount of assistance needed.	60	Requires occasional assistance, but is able to care for most of personal needs.				
	50	Requires considerable assistance and frequent medical care.				
	40	Disabled; requires special care and assistance.				
Unable to care for self; requires	30	Severely disabled; hospital admission is indicated although death not imminent.				
equivalent of institutional or hospital care; disease may be progressing rapidly.	20	Very sick; hospital admission necessary; active supportive treatment necessary.				
1 C C T J	10	Moribund; fatal processes progressing rapidly.				
	0	Dead				

Appendix 4. EuroQoL-5 Dimensions (EQ-5D)

By placing a checkmark in one box in each group below, please indicate which statements best describe your own health state today.

[figure not shown]
Mobility	
I have no problems in walking about	
I have some problems in walking about	
I am confined to bed	
Self-Care	
I have no problems with self-care	
I have some problems washing or dressing myself	
I am unable to wash or dress myself	
Usual Activities (e.g., work, study, housework, family, or leisure activities)	
I have no problems with performing my usual activities	
I have some problems with performing my usual activities	
I am unable to perform my usual activities	
Pain/Discomfort	
I have no pain or discomfort	
I have moderate pain or discomfort	
I have extreme pain or discomfort	
Anxiety/Depression Sample	
I am not anxious or depressed	
I am moderately anxious or depressed	
I am extremely anxious or depressed	

To help people say how good or bad a health state is, we have drawn a scale (rather like a thermometer) on which the best state you can imagine is marked 100 and the worst state you can imagine is marked 0.

We would like you to indicate on this scale how good or bad your own health is today, in your opinion. Please do this by drawing a line from the box below to whichever point on the scale indicates how good or bad your health state is today.

> Your own health state today

Sample

Appendix 5. Cockcroft-Gault Method for Estimating Creatinine Clearance

Formulas for calculating the estimated creatinine clearance (eC_{cr}) are provided in the table below. The formula appropriate to the units in which serum creatinine was measured and the subject's gender should be used.

Cockcroft-Gault Formulas for Calculating Estimated Creatinine Clearance

Serum Creatinine Units	Gender	Formula
mg/dL	Males	$\frac{eC_{cr}}{[mL/min]} = \frac{(140\text{-subject age [years]}) \times \text{subject weight [kilograms]} \times 1}{72 \times \text{subject serum creatinine [mg/dl]}}$
mg/dL	Females	$\frac{eC_{cr}}{[mL/min]} = \frac{(140\text{-subject age [years]}) \times \text{subject weight [kilograms]} \times 0.85}{72 \times \text{subject serum creatinine [mg/dl]}}$
μM/dL	Males	$\frac{eC_{cr}}{[mL/min]} = \frac{(140\text{-subject age [years]}) \times \text{subject weight [kilograms]} \times 1.23}{\text{Subject serum creatinine [mg/dl]}}$
µivi/UL	Females	$\frac{eC_{cr}}{[mL/min]} = \frac{(140\text{-subject age [years]}) \times \text{subject weight [kilograms]} \times 1.04}{\text{Subject serum creatinine [mg/dl]}}$

Abbreviation: eCcr=estimated creatinine clearance

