1. INTRODUCTION

1.1. Chronic Lymphocytic Leukemia

Chronic lymphocytic leukemia (CLL) is a neoplasia resulting from the progressive accumulation of functionally incompetent monoclonal B lymphocytes in blood, bone marrow, lymph nodes, spleen, and liver {Dighiero 2008}. CLL constitutes the most commonly occurring leukemia in Europe and the United States {Sant 2010, Surveillance Epidemiology and End Results (SEER) Program 2011}. While some patients never require treatment, many will need therapy for disfiguring or obstructing lymphadenopathy, debilitating constitutional B symptoms (fevers, night sweats, fatigue, weight loss) {Redaelli 2004}, or recurrent cytopenias and infections {Keating 2002b, Perkins 2002}. CLL is largely a disease of the elderly; at diagnosis, 70% of patients are ≥65 years of age and the median age is 72 years {Surveillance Epidemiology and End Results (SEER) Program 2011}.

In younger and relatively healthy patients with CLL, chemoimmunotherapy regimens that include the anti-CD20 monoclonal antibody, rituximab, are commonly employed to control disease manifestations {Gribben 2011}. Such combination therapies are effective in providing durable remissions {Byrd 2005, Fischer 2011, Hallek 2010, Iannitto 2011, Robak 2010}. However, while rituximab is usually well tolerated {Gentile 2010}, the chemotherapeutic agents (typically fludarabine, cyclophosphamide, or bendamustine) in such regimens are acutely cytotoxic, induce permanent bone marrow compromise, and can cause secondary malignancies {Carney 2010, Kyasa 2004, Tam 2008}. Furthermore, in elderly patients or in those with comorbid conditions, such regimens are associated with less efficacy and greater toxicity {Eichhorst 2009b, Goede 2011, Tam 2008}.

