Organ System	Parameter	Required Value	
Hepatic	Serum total bilirubin	≤1.5 x ULN (unless elevated due to Gilbert's syndrome)	
	Serum ALT	≤2.5 x ULN	
	Serum AST		
Renal	eCCra	>30 ml/min	
Pregnancy	β-HCGb	Negative	

- a As calculated by the Cockcroft-Gault formula (see Appendix 5) {Cockcroft 1976}
- b For women of child-bearing potential only; serum β-HCG must be negative during screening and serum β-HCG or urine dipstick pregnancy test must be negative at start of study treatment (Visit 2)

Abbreviations: β -HCG= beta human chorionic gonadotropin, ALT=alanine aminotransferase, AST=aspartate aminotransferase, eC_{Cr}=estimated creatinine clearance, ULN=upper limit of normal

- 8) For female subjects of childbearing potential, willingness to use a protocol-recommended method of contraception (as outlined in Section 5.6.4) from the screening visit (Visit 1) throughout the study and for 30 days following the last dose of study drug.

 Note: A female subject is considered to be of childbearing potential unless she has had a hysterectomy, bilateral tubal ligation, or bilateral oophorectomy; has medically documented ovarian failure (with serum estradiol and follicle-stimulating hormone [FSH] levels within the institutional postmenopausal range and a negative serum or urine βHCG), or is menopausal (age ≥54 with amenorrhea for >12 months or amenorrhea for >6 months with serum estradiol and FSH levels within the institutional postmenopausal range).
- 9) For male subjects of childbearing potential having intercourse with females of childbearing potential, willingness to use a protocol-recommended method of contraception (as outlined in Section 5.6.4) from the start of study drug (Visit 2) throughout the study and for 90 days following the last dose of study drug and to refrain from sperm donation from the start of study drug (Visit 2) throughout the study and for 90 days following the last dose of study drug. *Note: A male subject is considered able to father a child unless he has had a*

bilateral vasectomy with documented aspermia or a bilateral orchiectomy, or has ongoing testicular suppression with a depot luteinizing hormone-releasing hormone (LH-RH) agonist (eg, goserelin acetate [Zoladex[®]]), leuprolide acetate [Lupron[®]]), or triptorelin pamoate [Trelstar[®]]).

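### Two Cockcroft-Gault rows in Appendix 5 carry units that do not fit their constants; used with either printed unit, they overstate creatinine clearance about 10-fold or 88-fold

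*Protocol*

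**What the plan says.** Inclusion criterion 7 (Protocol 4.2.1, Table 4-1) requires an estimated creatinine clearance above 30 mL/min. The table's footnote gives the method: "As calculated by the Cockcroft-Gault formula (see Appendix 5").

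Appendix 5 offers four formulas, by unit and sex, and tells the reader to use "The formula appropriate to the units in which serum creatinine was measured" and the subject's sex. All four share the numerator (140 - age) x weight.

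- Rows 1 and 2 (mg/dL): sex factor 1 or 0.85, divided by 72 x creatinine.
- Rows 3 and 4: constant 1.23 or 1.04, divided by creatinine alone, without the 72. The male label reads μM/dL. The female label is garbled in the extracted text and presumably says the same.

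Apart from a capital letter, the denominator text in rows 3 and 4 is the same as in rows 1 and 2: "subject serum creatinine [mg/dl".

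**The concern.** Rows 3 and 4 contradict themselves, because the label names one unit and the denominator another. Neither unit suits constants from which the 72 has been removed. The constants look like those for creatinine in micromol/L, a unit that the appendix does not print.

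This matters because the appendix is the stated method for a numerical eligibility limit that investigators may not waive (Protocol 4.2). Protocol 4.3 says the baseline laboratory limits are there to keep out subjects with serious organ compromise. Sites are in the United States and Europe, so some use of SI units is plausible. An inflated clearance errs in the unsafe direction, because it admits subjects whom the limit is meant to exclude.

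**Working it through.** **Inputs from the documents.** mg/dL rows: factor 72, sex factor 1 or 0.85. Rows 3 and 4: constants 1.23 and 1.04. Limit: above 30 mL/min.

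**Assumptions.** Creatinine molar mass is 113.12 g/mol, so 1 mg/dL = 88.40 micromol/L = 8.84 micromol/dL. The label μM/dL is read as micromol/dL. The example subject is 72 years old and weighs 70 kg, with creatinine 3.0 mg/dL. The age is taken from Protocol 1.1, where "the median age is 72 years" describes CLL patients at diagnosis, not this trial's subjects. The fold errors below do not depend on age, weight or creatinine.

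**Step 1: reproduce the constants from the mg/dL rows.**
- Males: 88.40/72 = 1.228, printed as 1.23.
- Females: 0.85 x 88.40/72 = 1.044, printed as 1.04.

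So the constants are right, for micromol/L.

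**Step 2: check with the protocol's figures alone.** For rows 3 and 4 to agree with rows 1 and 2, the number entered for creatinine must exceed its mg/dL value by:
- Males: 1.23 x 72 = 88.56.
- Females: 1.04 x 72/0.85 = 88.09.

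Neither printed unit provides that factor: mg/dL gives 1 and micromol/dL gives 8.84.

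**Step 3: overstatement relative to the mg/dL rows.**

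| Unit entered in rows 3 and 4 | Males | Females |
|---|---|---|
| micromol/L (not printed) | 88.56/88.40 = 1.00 | 88.09/88.40 = 1.00 |
| micromol/dL (label) | 88.56/8.84 = 10.02 | 88.09/8.84 = 9.97 |
| mg/dL (denominator) | 88.56 | 88.09 |

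**Step 4: true clearance at which the printed limit would act.**
- micromol/dL: 30/10.02 = 2.99 mL/min (males); 30/9.97 = 3.01 (females).
- mg/dL: 30/88.56 = 0.339 mL/min (males); 30/88.09 = 0.341 (females).

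**Step 5: example, male.** Numerator: (140 - 72) x 70 = 4760. Creatinine: 3.0 mg/dL = 265.2 micromol/L = 26.52 micromol/dL.
- mg/dL row: 4760/(72 x 3.0) = 22.0 mL/min, fails.
- Row 3, micromol/L: 4760 x 1.23/265.2 = 22.1, fails.
- Row 3, micromol/dL: 4760 x 1.23/26.52 = 221, passes.
- Row 3, mg/dL: 4760 x 1.23/3.0 = 1952, passes.

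For this man the limit should exclude at 4760/(72 x 30) = 2.2 mg/dL or above. With the printed units, exclusion would need about 22 mg/dL (micromol/dL) or 195 mg/dL (mg/dL).

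**The case against.** A reader might infer that the renal limit excluded nobody, or that subjects with severe renal impairment were enrolled. The documents support neither reading, for these reasons:

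- The mg/dL rows are correct, so a site using them applies the limit properly. A site that ignores the label and enters a micromol/L value in row 3 or 4 also gets the right answer.
- The 88-fold error needs an mg/dL value in a row that the appendix assigns to another unit. The 10-fold error needs a value in micromol/dL, and neither document says that any laboratory here reports in that unit. A result such as 1952 mL/min would probably prompt a query.
- Even with the 10-fold error, a true clearance of about 3 mL/min or less still fails. A woman of 90 years and 40 kg with 8 mg/dL has 50 x 40 x 0.85/(72 x 8) = 2.95 mL/min, and row 4 with micromol/dL gives 50 x 40 x 1.04/70.72 = 29.4.
- The limit belongs to the criteria for entry after progression. The shorter list for subjects transferring when the primary study stops early (Protocol Synopsis; SAP 1.2) has no laboratory criterion. SAP 3.5.1 says the primary study did stop early, and SAP 1.3 gives 161 as actual enrolment, so few if any future decisions depend on the formula.
- Benefit-risk judgement (inclusion criterion 10) and the exclusion for significant illness or laboratory abnormality (exclusion criterion 6) also apply to entry after progression.
- The unit column is damaged in the extracted text.

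Most of this stands, and it limits the consequence. It does not make the printed rows right. The clinical-judgement criteria do not replace a numerical limit. The finding does not need the garbled female label: the male label and both denominators are legible, and neither printed unit fits the constants.

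**Conclusion.** Rows 3 and 4 of Appendix 5 are wrong as printed. Their constants hold for creatinine in micromol/L, and neither printed unit is that. Anyone using these rows with a printed unit overstates clearance about 10-fold or about 88-fold, and the limit of 30 mL/min then excludes practically nobody assessed that way.

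The 88-fold figure follows from the protocol's own constants. The 10-fold figure also needs the molar mass and the reading of μM/dL as micromol/dL.

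How often this happened cannot be known from the documents. They do not say who calculated clearance, which row was used, or in which unit creatinine was reported. The 161 enrolled subjects include both entry routes. The only relevant group size given is 4, for those who progressed on idelalisib and moved to 300 mg BID (SAP 3.5.1). No endpoint, dose-modification rule in Table 5-2 or SAP analysis uses estimated clearance, so no estimate changes. What remains is a safety-relevant error in an eligibility formula, whose main value now is as a reason to check past calculations.

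**What to change.** In Appendix 5, change the unit label and both denominators of the rows with constants 1.23 and 1.04 to micromol/L. The constants, the mg/dL rows and the clinical limit stay as they are.

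Then identify subjects who entered after progression and whose clearance was calculated with these rows. Recompute it from recorded age, sex, weight and screening creatinine, and report any value at or below 30 mL/min as an eligibility deviation. Where the row used was not recorded, recompute for all such subjects.

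The text change is a few table cells. The recheck uses data already collected at screening (Protocol Table 6-1) and needs no new procedure.
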